Date of last protocol update: December 11, 2015 Principal Investigator: [name] PhD

Proof of Concept Study of the Effectiveness of Ozurdex in lieu of Oral Corticosteroids for the Control of Active Intermediate and Posterior Uveitis Requiring Immunosuppressive Drug Therapy

NCT02049476

JHM IRB - eForm A - Protocol

- Use the section headings to write the JHM IRB eForm A, inserting the appropriate material in each. If a section is not applicable, leave heading in and insert N/A.
- When submitting JHM IRB eForm A (new or revised), enter the date submitted to the field at the top of JHM IRB eForm A.

1. **Abstract** (Provide no more than a one page research abstract briefly stating the problem, the research hypothesis, and the importance of the research.) See background.

2. Objectives:

This is a single arm proof of concept study evaluating whether or not the dexamethasone pellet (Ozurdex®, Allergan, Irvine, CA) can replace oral corticosteroid (e.g. prednisone) in the treatment of active sight-threatening, noninfectious intermediate or posterior uveitis in which immunosuppressive drug therapy is indicated.

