3. **Background:** Intermediate and posterior uveitis are thought to be severe intraocular inflammation that may lead to permanent visual loss. It is estimated that these forms of uveitis comprise the fifth or sixth leading cause of blindness and tend to affect working class age patients, thus causing loss of work hours and diminished productivity and quality of life. Because the posterior segment of the eve is not adequately treated by corticosteroid drops often systemic drug therapy is used including oral corticosteroids or prednisone. Prednisone can have a myriad of side effects in approximately onequarter to one-third of cases treated in tertiary care centers such as ours, additional medications such as immunosuppressive drugs are required to control the disease and/or to allow for appropriate tapering of oral prednisone to subsequent levels that have a low side effect profile when delivered over a long period of time. Typically, chronic prednisone therapy in doses of 7.5 mg daily or less are thought to have a low enough side effect profile to be amenable to long-term therapy. However frequently immunosuppressive drugs are required to get the dosing to this level. There are occasions when patients are intolerant of any dose of oral corticosteroids or are intolerant of the higher doses of oral corticosteroids (30 - 60 mg daily) and therefore this treatment modality is avoided due to prednisone's attendant side effects. Although periocular and intravitreal corticosteroids injections may be performed, with these modalities the standard of care is to wait until the disease reactivates before instituting such therapy and therefore a chronic suppressive dose is not obtained. fluocinolone acetonide implant (Retisert®, Bausch and Lomb, Tampa, FL) is FDA-approved for the treatment of intermediate and posterior uveitis and it is equally effective in controlling uveitis as highdose oral corticosteroids but avoids the systemic side effects associated with the use of high doses of oral corticosteroids. However, this form of local therapy has high rates of ocular side effects, including ocular hypertension causing glaucoma and/or requiring glaucoma surgery and cataracts. Furthermore, every two and half to three years the implant is exhausted of corticosteroid and therefore repeat surgical insertion of another implant may be required. A useful potential therapy for the treatment of these patients would be a shorter-acting local corticosteroid that could be delivered in conjunction with systemic immunosuppressive drug therapy that would have a lower ocular side effect profile but still would be effective enough to replace the use of high-dose systemic corticosteroids in the treatment of active intermediate or posterior uveitis. It is possible that the dexamethasone pellet could fill this unique role in the treatment of uveitis. We propose this proof of concept study to evaluate dexamethasone pellet for this specific use among patients with active intermediate and posterior uveitis.

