- Possibility of repeat dexamethasone pellet insertion o Adverse events related to the procedure will be collected (e.g., vitreous hemorrhage, elevated IOP, retinal detachment)
- 6-month examination o Interval treatment history (current therapies for the treatment of uveitis, history of corticosteroid use including periocular corticosteroids, history of immunosuppressive drug use, need for IOP-lowering medications)
 - Interval ocular history (any complications due to uveitis, any ocular surgeries or procedures, history of glaucoma or ocular hypertension, treatment to lower intraocular pressure including laser procedures and/or surgeries
 - Ophthalmic examination including best-corrected visual acuity, IOP measurement, presence and degree of uveitis activity, presence of ocular complications including cystoid macular edema (CME), findings of slit lamp examination including presence and degree of cataract, findings of fundoscopic examination including cup to disc ratio.
 - Results of OCT and fluorescein angiography testing as clinically indicated o NEI-VFQ and EuroQoL administered.
 - o Adverse event reporting
- Possibility of repeat dexamethasone pellet insertion or treatment with best medical judgment of Adverse events related to the procedure will be collected (e.g., vitreous hemorrhage, elevated IOP, retinal detachment)
- 9-month examination o Interval treatment history (current therapies for the treatment of uveitis, history of corticosteroid use including periocular corticosteroids, history of immunosuppressive drug use, need for IOP-lowering medications)
 - o Interval ocular history (any complications due to uveitis, any ocular surgeries or procedures, history of glaucoma or ocular hypertension, treatment to lower intraocular pressure including laser procedures and/or surgeries
 - Ophthalmic examination including best-corrected visual acuity, IOP measurement, presence and degree of uveitis activity, presence of ocular complications including cystoid macular edema (CME), findings of slit lamp examination including presence and degree of cataract, findings of fundoscopic examination including cup to disc ratio.

- o Results of OCT and fluorescein angiography testing as clinically indicated o NEI-VFQ and EuroQoL administered.
- o Adverse event reporting

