- Possibility of repeat dexamethasone pellet insertion or treatment with best medical judgment of Adverse events related to the procedure will be collected (e.g., vitreous hemorrhage, elevated IOP, retinal detachment)
- **12-month examination** O Interval treatment history (current therapies for the treatment of uveitis, history of corticosteroid use including periocular corticosteroids, history of immunosuppressive drug use, need for IOP-lowering medications)
 - Interval ocular history (any complications due to uveitis, any ocular surgeries or procedures, history of glaucoma or ocular hypertension, treatment to lower intraocular pressure including laser procedures and/or surgeries
 - Ophthalmic examination including best-corrected visual acuity, IOP measurement, presence and degree of uveitis activity, presence of ocular complications including cystoid macular edema (CME), findings of slit lamp examination including presence and degree of cataract, findings of fundoscopic examination including cup to disc ratio.
 - Visual field assessment
 - Slit lamp photographs to assess cataract
 - Optic nerve photos
 - o Results of OCT and fluorescein angiography testing as clinically indicated o NEI-VFQ and EuroQoL administered.
 - o Adverse event reporting
- Extended follow-ups o Patients will continue to be followed at 3 month intervals after M12 according to standard of care until the common study close-out which will occur after the 2 year follow-up of the 20th enrolled patient
- Possibility of repeat dexamethasone pellet insertion or treatment at each of the 3 month extended follow-ups with best medical judgment o Adverse events related to the procedure will be collected (e.g., vitreous hemorrhage, elevated IOP, retinal detachment)
- b. Study duration and number of study visits required of research participants.
 - Patients will be followed for a minimum period of 12 months.
 - A minimum of 9 visits (BL, Day 14, M1, M2, M3, M6, M9, and M12). If the PI/study ophthalmologist decides to insert another dexamethasone pellet, s/he may do so at M3, and/or M6, and/or M9, and/or at 3 month intervals thereafter (until the common study closeout) if indicated with best medical judgment
- c. Blinding, including justification for blinding or not blinding the trial, if applicable.
 - N/A
- d. Justification of why participants will not receive routine care or will have current therapy stopped.

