 - N/A. Use of the dexamethasone pellet and immunosuppressive drug therapy are each part of standard clinical care in the treatment of active intermediate and posterior uveitis. The dexamethasone pellet is FDA-approved for the treatment of intermediate and posterior uveitis.
- e. Justification for inclusion of a placebo or non-treatment group.
 - N/A. There is no placebo or non-treatment arm in this pilot study.
- f. Definition of treatment failure or participant removal criteria.
 - N/A
- g. Description of what happens to participants receiving therapy when study ends or if a participant's participation in the study ends prematurely.

- Since all treatments are currently used in the clinical care of uveitis patients, all patients enrolled in this study will be able to continue receiving therapy according to best medical judgment once the study ends.

5. Inclusion/Exclusion Criteria Inclusion Criteria:

- Active sight-threatening intermediate or posterior uveitis for which immunosuppressive drug therapy is planned and the physician is considering treatment with high-dose corticosteroid to control the uveitis whilst immunosuppressive drugs are being instituted or adjusted.
 - o Note: it is acceptable for the patient to already be on an immunosuppressive drug as long as high dose corticosteroids are indicated.
- Patients must be age 18 years or older (the dexamethasone pellet is not FDA-approved for pediatric use) and sign an informed consent.
- The ocular media must be clear enough to obtain OCT and fundus photographs.
- No elective intraocular surgery should be planned for the first 3 months after enrollment.

Exclusion Criteria:

- Infectious uveitis
- History of scleritis
- Active or suspected viral infection of the cornea or conjunctiva
- History of mycobacterial or fungal disease
- HIV positivity
- Age <18 years old
- Allergy to dexamethasone
- Uncontrolled IOP
- Advanced glaucoma
- Aphakia with rupture of the posterior lens capsule
- ACIOL with rupture of the posterior lens capsule
- Media opacity that would preclude evaluation of the posterior pole via fundus photography or OCT assessment
- Planned elective ocular surgery within 3 months of enrollment Any systemic disease requiring systemic corticosteroids.

6. Drugs/ Substances/ Devices

a. The rationale for choosing the drug and dose or for choosing the device to be used.

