The fluocinolone acetonide implant is FDA-approved for the treatment of intermediate and posterior uveitis and it is equally effective in controlling uveitis as high-dose oral corticosteroids but avoids the systemic side effects associated with the use of high doses of oral corticosteroids. However, this form of local therapy has high rates of ocular side effects, including ocular hypertension causing glaucoma and/or requiring glaucoma surgery and cataracts. Furthermore, every two and half to three years the implant is exhausted of corticosteroid and therefore repeat surgical insertion of another implant may be required. A useful potential therapy for the treatment of these patients would be a shorter-acting local corticosteroid that could be delivered in conjunction with systemic immunosuppressive drug therapy that would have a lower ocular side effect profile but still would be effective enough to replace the use of high-dose systemic corticosteroids in the treatment of active intermediate and posterior uveitis. It is possible that the dexamethasone pellet could fill this unique role in the treatment of uveitis. We propose this proof of concept study to evaluate the dexamethasone pellet for this specific use among patients with active intermediate and posterior uveitis.

b. Justification and safety information if FDA approved drugs will be administered for non-FDA approved indications or if doses or routes of administration or participant populations are changed.

- N/A
- c. Justification and safety information if non-FDA approved drugs without an IND will be administered.
- N/A. The dexamethasone pellet is FDA-approved for the treatment of intermediate and posterior uveitis.

7. Study Statistics

- a. Primary outcome variable.
 - Control of uveitis at the 1 month, 2 month, 3 month, 6 month and 12 month time points. Cumulative incidences of uveitis control will be compared to historical data from the Johns Hopkins cohort and from the Systemic Immunosuppressive Treatment of Eye Diseases (SITE) Research Group.
- b. Secondary outcome variables.

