 - The cumulative incidence of control of inflammation (0.5+ or less vitreous cells in the liquid vitreous; trace or less anterior chamber cells; and inactive chorioretinal lesions) at the 3month visit and the 6-month visit will be compared to the published data (from Johns Hopkins and from the SITE database) of the cumulative incidence of steroid-sparing success (prednisone <=7.5 mg daily and controlled disease) and of oral steroid discontinuation with the goal of proving NON-INFERIORITY of the dexamethasone pellet. Cumulative incidences of ocular and systemic side effects of the dexamethasone pellet will be compared to those of oral prednisone via rates and cumulative incidences at 12 months.
- c. Statistical plan including sample size justification and interim data analysis.
 - 20 patients will be enrolled and the data regarding success of control of uveitis at the 6 and 12 month examinations will be compared with historical published data. Comparative data from the Johns Hopkins cohort, SITE database, and published MUST data will be utilized. d. Early stopping rules.
- None

8. Risks

- a. Medical risks, listing all procedures, their major and minor risks and expected frequency.
 - Dexamethasone pellet insertion within 14 days of the baseline visit and potential insertion at months 3, 6, 9, and every 3 months thereafter based on the study protocol and clinical judgment of the PI/study ophthalmologist.
 - Dexamethasone pellet should not be used if patient is allergic to any of its ingredients.
 - Injections into the vitreous in the eye may be associated with eye inflammation, subconjunctival hemorrhage, and transient increased eye pressure. Rarely, intravitreal injections may be associated with vitreous hemorrhage, retinal detachment, or endophthalmitis. The risk of performing an intravitreal injection as part of this study is no greater than that associated with clinical care in the treatment of uveitis. The study ophthalmologist will monitor the patient regularly after each injection.

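### Section 7b scores pellet patients on inflammation control alone but the historical benchmark on control plus prednisone at or below 7.5 mg daily; on the prednisone term, this can only favour the pellet or have no effect

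*Combined protocol and SAP*

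**What the plan says.** All references are to the combined protocol and SAP.

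- **Section 7b, study side.** The outcome begins "The cumulative incidence of control of inflammation (0.5+ or less vitreous cells in the liquid vitreous; trace or less anterior chamber cells" and adds inactivity of chorioretinal lesions. It has no prednisone term. It is assessed at months 3 and 6.
- **Section 7b, historical side.** The comparators are published rates of "steroid-sparing success (prednisone <=7.5 mg daily and controlled disease) and of oral steroid discontinuation with the goal of proving NON-INFERIORITY of the dexamethasone pellet".
- **Title.** The study concerns "Effectiveness of Ozurdex in lieu of Oral Corticosteroids". The objective in Section 2 is likewise replacement of oral corticosteroid.
- **Section 6a.** The rationale is a local steroid "effective enough to replace the use of high-dose systemic corticosteroids in the treatment of active intermediate and posterior uveitis". Section 3 describes some patients as "intolerant of the higher doses of oral corticosteroids (30 - 60 mg daily") and treats 7.5 mg daily or less as acceptable for long-term use.
- **Item 4d.** The template asks for "Justification of why participants will not receive routine care or will have current therapy stopped". The answer begins "N/A. Use of the dexamethasone pellet and immunosuppressive drug therapy are each part of standard clinical care" and names no prednisone taper or stop.
- **Item 4f and Section 5.** Treatment failure is not applicable. The only exclusion that concerns systemic corticosteroids is for a systemic disease that needs them.
- **Section 4a, between months 3 and 6.** The only treatment entry is "Possibility of repeat dexamethasone pellet insertion o Adverse events related to the procedure will be collected".

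**The concern.** A comparison meant to prove non-inferiority needs one success rule on both sides. Here a historical patient succeeds only with quiet disease and a low prednisone dose, while a study patient succeeds with quiet disease at any dose. A study patient controlled only while taking more than 7.5 mg would count for the pellet, although a historical patient in the same state would count as a failure.

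The stake is the study's own question. A patient who needs prednisone above the level the plan calls suitable for long-term use has not shown that the pellet replaces it. A non-inferiority result against the steroid-sparing benchmark could rest partly on such patients, and the 7b endpoint would not show it.

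**Working it through.** There is no figure in the plan to reproduce. The sample size of 20 comes without a margin, alpha, power, benchmark rate or expected rate.

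**Step 1. The two definitions side by side**

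| | Study patients | Steroid-sparing benchmark |
|---|---|---|
| Inflammation | vitreous cells, anterior chamber cells, lesion activity | controlled disease, not further defined |
| Prednisone | no condition | 7.5 mg daily or less |

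**Step 2. Direction, prednisone term only**

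Let T1 be the first visit with control, and T2 the first visit with control and prednisone at or below 7.5 mg. Then T1 ≤ T2 for every patient, so cumulative control is never below the cumulative composite.

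The same follows from listing every path over the visits at months 1, 2, 3 and 6. Each visit has four states (control yes/no, low dose yes/no), which gives 4^4 = 256 paths:

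- The composite is never reached on 3^4 = 81 paths, and control is never reached on 2^4 = 16 of these. Control without the composite: 81 − 16 = 65.
- Composite without control: 0.
- Same result on both: 256 − 65 = 191.

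To month 3 there are 4^3 = 64 paths, and the counts are 27 − 8 = 19, then 0, then 64 − 19 = 45. These are logical counts, not probabilities.

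**Step 3. Does the plan force the gap to zero?**

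It would be zero if every controlled study patient had also met the composite by that time. The title and the pellet-only entry between months 3 and 6 show that this is intended. Nothing enforces it. Items 4d and 4f set no prednisone rule, the exclusion concerns systemic disease, and the endpoint has no dose term. Control on a dose above 7.5 mg but below 30 mg would be compatible with replacing high-dose steroid and would count as a success, yet would miss the benchmark.

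**Step 4. Size (assumed counts)**

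Let k be the number of patients counted as controlled by a visit who have never had both parts together up to then. Scoring all 20 by patient with no dropout, the gap is k/20, or 5 points × k. With 14 of 20 controlled by month 6 (exact Clopper-Pearson 95% intervals):

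| k | Composite | Rate | 95% CI |
|---|---|---|---|
| 0 | 14/20 | 70% | 45.7–88.1 |
| 1 | 13/20 | 65% | 40.8–84.6 |
| 2 | 12/20 | 60% | 36.1–80.9 |
| 3 | 11/20 | 55% | 31.5–76.9 |

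Starting from 12/20, k = 3 takes 60% (36.1–80.9) to 45% (23.1–68.5). Starting from 16/20, it takes 80% (56.3–94.3) to 65% (40.8–84.6). The half-width at 14/20 is (88.1 − 45.7)/2 ≈ 21 points, so these shifts lie within sampling error.

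Counting patients above 7.5 mg at the visit itself gives only an upper bound on their contribution to k. Of the 64 + 56 = 120 paths controlled by month 6 with a high dose at month 6, 37 + 37 = 74 had already met the composite. If 4 of the 14 are above 7.5 mg at month 6 and 4, 2 or 0 of them met both parts before, they add 0, 10 or 20 points.

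**Step 5. What it could do to a non-inferiority test (all inputs assumed)**

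Take a fixed benchmark of 0.60, a margin of 0.15 and one-sided alpha of 0.025. The limit is 0.60 − 0.15 = 0.45, and success needs at least 14 of 20, since P(X ≥ 14 | 20, 0.45) = 0.021. Let the pellet's true composite rate sit exactly at the limit, and let q be the share of controlled patients who meet the composite. Scored on control, the success rate is 0.45/q.

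| q | Rate on control | Chance of false non-inferiority |
|---|---|---|
| 1 | 0.450 | 0.021 |
| 0.9 | 0.500 | 0.058 |
| 0.8 | 0.563 | 0.155 |
| 0.7 | 0.643 | 0.391 |

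At q = 0.8, benchmarks of 0.4–0.7 and margins of 0.10–0.20 give 0.041 to 0.225.

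**The case against.** The strongest reply is that the mismatch is empty by design. The objective is replacement of oral corticosteroid, 7b goes on to compare side effects with those of oral prednisone, and Section 9 hopes for equal effect without the systemic side effects. All this presupposes patients who are largely off prednisone, for whom control is already steroid-sparing control. This stands as a description of intent, and it is why the effect may be zero. It is not a scoring rule.

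Four further points have force:

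- Item 4d is a template question, so its answer is weak evidence that prednisone may continue. Its relevance is only that it supplies no taper or stop.
- The 30–60 mg range is background text, not an entry or endpoint threshold. The wording on best medical judgment first appears after the 6-month examination, so it is not relied on here.
- The path count only confirms that meeting both parts implies meeting one. It says nothing about how often the gap will arise.
- 7b is one secondary comparison in a 20-patient proof-of-concept study. The absent margin and alpha limit it more deeply than this mismatch does.

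These points limit the weight of the concern. They do not remove the mismatch, and sampling error does not excuse it, since noise can go either way and the prednisone term cannot.

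**Conclusion.** The concern holds and should be fixed. On the prednisone term, the direction is certain by logic: in the pellet's favour, or nil. The size is unknown, at 5 points per affected patient out of 20, and nil in the intended case.

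The result has three limits:

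- The net sign of the whole comparison is not fixed, because the historical definition of controlled disease may be looser or stricter than the plan's three criteria.
- For the oral steroid discontinuation benchmark the direction is unknown, since 7b does not say whether control is also required there.
- With no margin or alpha stated, no decision can be shown to flip. The rates of false non-inferiority above are illustrations on assumed inputs.

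**What to change.** In Section 7b:

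1. For the steroid-sparing comparison at months 3 and 6, score study patients on the plan's inflammation criteria together with oral prednisone at or below 7.5 mg daily.
2. Fix one timing rule before analysis: date success from the first visit at which both parts hold, or use the published source's rule if it differs.
3. State the source's definition of controlled disease beside the plan's criteria.
4. Compare oral steroid discontinuation separately, with one definition on both sides.
5. Report control regardless of prednisone as supportive, with the number of controlled patients above 7.5 mg and the number who never met both parts together.

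This is an analysis definition, not a treatment rule, and it leaves the primary outcome in 7a unchanged. It costs revised wording and one extra tabulation. Current therapies and corticosteroid history are already collected at each scheduled examination, but daily prednisone dose is not listed, so its capture must be confirmed or a field added. The reported 7b success rate may be lower. If every controlled patient has met both parts together, the result does not change and replacement is shown rather than presumed.

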 - Ophthalmic examination including best-corrected visual acuity, IOP measurement, presence and degree of uveitis activity, presence of ocular complications including cystoid macular edema (CME), findings of slit lamp examination including presence and degree of cataract, findings of fundoscopic examination including cup to disc ratio.
 - o Results of OCT and fluorescein angiography testing if clinically indicated o NEI-VFQ and EuroQoL administered.
 - o Adverse event reporting
- 2-month examination o Interval treatment history (current therapies for the treatment of uveitis, history of corticosteroid use including periocular corticosteroids, history of immunosuppressive drug use, need for IOP-lowering medications)
 - Interval ocular history (any complications due to uveitis, any ocular surgeries or procedures, history of glaucoma or ocular hypertension, treatment to lower intraocular pressure including laser procedures and/or surgeries

- Ophthalmic examination including best-corrected visual acuity, IOP measurement, presence and degree of uveitis activity, presence of ocular complications including cystoid macular edema (CME), findings of slit lamp examination including presence and degree of cataract, findings of fundoscopic examination including cup to disc ratio.
- Results of OCT and fluorescein angiography testing if clinically indicated o NEI-VFQ and EuroOoL administered.
- o Adverse event reporting
- 3-month examination o Interval treatment history (current therapies for the treatment of uveitis, history of corticosteroid use including periocular corticosteroids, history of immunosuppressive drug use, need for IOP-lowering medications)
 - o Interval ocular history (any complications due to uveitis, any ocular surgeries or procedures, history of glaucoma or ocular hypertension, treatment to lower intraocular pressure including laser procedures and/or surgeries
 - Ophthalmic examination including best-corrected visual acuity, IOP measurement, presence and degree of uveitis activity, presence of ocular complications including cystoid macular edema (CME), findings of slit lamp examination including presence and degree of cataract, findings of fundoscopic examination including cup to disc ratio.
 - o Results of OCT and fluorescein angiography testing if clinically indicated o NEI-VFQ and EuroQoL administered.
 - o Adverse event reporting

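### Section 7b's secondary non-inferiority goal has no margin or decision rule and pairs unlike endpoints, so a claim under it is not reliably supported unless the lower confidence bound exceeds the historical rate on a matched endpoint

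*Combined protocol and SAP*

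**What the plan says.** Section 7b (secondary outcomes) scores study patients at 3 and 6 months on cumulative incidence of "control of inflammation (0.5+ or less vitreous cells in the liquid vitreous; trace or less anterior chamber cells; and inactive chorioretinal lesions"; no prednisone condition enters that definition. The published Johns Hopkins and SITE figures set beside it are the cumulative incidences of "steroid-sparing success (prednisone <=7.5 mg daily and controlled disease) and of oral steroid discontinuation". The comparison is made "with the goal of proving NON-INFERIORITY of the dexamethasone pellet".

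Section 7a (primary outcome) says "Cumulative incidences of uveitis control will be compared to historical data from the Johns Hopkins cohort" and from SITE, without a decision rule and without claiming non-inferiority. Section 7c says "20 patients will be enrolled" and that control at 6 and 12 months will be compared with published data, with MUST added as a source. Neither section gives a margin, alpha, test, confidence level or historical rate.

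On oral prednisone during the study:
- Section 4d, headed "Justification of why participants will not receive routine care or will have current therapy stopped", is answered N/A.
- Section 4f, on treatment failure and removal, is also N/A.
- Section 4a records at each follow-up visit an "Interval treatment history (current therapies for the treatment of uveitis, history of corticosteroid use including periocular corticosteroids". Dose is not named.
- Section 4e confirms the lack of a concurrent comparator: "There is no placebo or non-treatment arm in this pilot study".

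**The concern.** A non-inferiority conclusion needs one endpoint measured on both sides, a reference value, a margin and a confidence bound that clears reference minus margin. Section 7b supplies none of these.

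The endpoint pairing matters most because the study asks whether the pellet can replace oral corticosteroid (section 2), and section 9a hopes for a treatment that matches oral prednisone. Under the 7b definition, a patient whose eye is quiet while taking more than 7.5 mg of prednisone daily counts as a study success but would not count in the published steroid-sparing figure. A finding of non-inferiority could then come partly from patients in whom prednisone had not been replaced. With no margin stated, the same data could also be called non-inferior or not, depending on a number chosen afterwards.

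**Working it through.** **Inputs.** From the documents: n = 20, a single arm, and the endpoint definitions in 7b. Assumed, because the documents give none: historical rate P0 (50% to 70%, treated as known), margin M, one-sided alpha 0.025, one binary result per patient and nobody lost. Section 4a allows implants in both eyes and the control criteria are eye findings, but no unit of analysis is stated. The figure of 20 can be neither reproduced nor refuted, since 7c gives no inputs for it.

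**1. Direction of the mismatch.** Let C be control and D be prednisone at or below 7.5 mg daily. In the same patients, P(C) = P(C and D) + P(C and not D), so P(C) is never below P(C and D). Against steroid-sparing success the mismatch is therefore k = P(C and not D), which is zero or favours the pellet. It is zero if every controlled patient is at or below 7.5 mg. This takes controlled disease to mean the same on both sides. Discontinuation, as worded, states no control requirement, so neither event contains the other and the direction is unknown.

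**2. Precision with 20 patients** (no historical rate needed). Exact (Clopper-Pearson) 95% lower bound, which solves P(X ≥ x | p) = 0.025:

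| Observed | Lower bound | Gap in points |
|---|---|---|
| 10/20 (50%) | 27.2% | 22.8 |
| 12/20 (60%) | 36.1% | 23.9 |
| 14/20 (70%) | 45.7% | 24.3 |
| 16/20 (80%) | 56.3% | 23.7 |
| 18/20 (90%) | 68.3% | 21.7 |
| 19/20 (95%) | 75.1% | 19.9 |

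A result equal to history thus excludes only deficits larger than about 20 to 24 points. For 14/20 the full exact interval is 45.7% to 88.1%. A log-log cumulative-incidence interval without censoring is 49.9% to 87.7%.

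**3. The verdict depends on the unstated margin.** Take 14/20 and an assumed P0 of 60%. With M = 15 the bar is 60 − 15 = 45%, and 45.7% clears it. With M = 10 the bar is 50%, and 45.7% does not.

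**4. Illustrative power, endpoints matched and true rates equal.** The rule is non-inferior if the lower bound exceeds P0 − M; power is P(X ≥ r | p = P0), where r is the smallest count that passes. Over P0 of 50% to 70% in 1-point steps:

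| Margin (points) | Power |
|---|---|
| 10 | 6–14% |
| 15 | 14–28% |
| 20 | 28–45% |
| 25 | 45–66% |
| 30 | 67–83% |

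The smallest whole-point margin giving 80% power is 29 to 35 points across that range. If the pellet is truly 20 or 25 points better than history, power at a 10-point margin is 65–87% or 82–98%.

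**5. Illustrative effect of the mismatch.** Suppose M = 15 and the pellet is truly 15 points worse on the matched steroid-sparing endpoint. Its scored rate is P0 − 15 + k. At P0 = 60% the rule is r = 14 (13/20 has lower bound 40.8%, below 45%). With k = 0 the scored rate is 45% and P(X ≥ 14) = 2.1%. With k = 10 it is 55% and 13.0%. Over P0 of 50% to 70%:

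| Assumed k (points) | Chance of passing |
|---|---|
| 0 | 0.8–2.5% |
| 5 | 2–7% |
| 10 | 6–15% |
| 15 | 14–28% |
| 20 | 27–45% |

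The documents support no particular value of k.

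**The case against.** The best defence is design intent. The title and section 2 present the pellet as a substitute for oral corticosteroid, the inclusion criteria select patients for whom high-dose steroid is being considered, and section 5 excludes systemic disease that needs systemic steroid. On that reading most controlled patients would be at low or no prednisone, k would be small, and the larger values in the last table look unlikely. The N/A in 4d is also weak evidence: the text after it speaks of the pellet and immunosuppressive drugs as standard care and says nothing about continuing prednisone.

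This much stands: the mismatch may prove to be nil. But no passage bars oral prednisone for the uveitis or counts its use as failure, and sections 4a and 4b leave treatment at later visits to clinical judgment. The endpoint does not secure what the title implies, and the discontinuation comparison would pair unlike events in any case.

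Two stronger readings might be inferred, and neither is supported:
- *No result could ever establish non-inferiority.* A lower bound above the historical rate implies non-inferiority at every margin. For example, 17/20 has a lower limit of 62.1%, above an assumed 60%. If every controlled patient were at or below 7.5 mg, that would support the steroid-sparing comparison.
- *The sample size is wrong.* This is a 20-patient pilot, no stopping rule depends on 7b, and the power figures rest on assumed rates and margins.

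It is also fair that corticosteroid use and current therapies are already recorded. No case report form is in the documents, so a missing dose field is not shown.

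**Conclusion.** The concern holds. Section 7b states a goal of proof without a margin, confidence level, reference rate or decision rule, and it measures different things on the two sides. The steroid-sparing comparison is neutral or biased towards the pellet; the discontinuation comparison is not like for like. A non-inferiority claim under 7b is not reliably supported unless the lower confidence bound exceeds the historical rate on a matched endpoint.

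The firmest figure is the 20 to 24 point gap between an observed result of 10/20 to 19/20 and its exact 95% lower bound, which assumes only one binary result per patient and no losses. The power and inflation figures are illustrations, not findings about this trial.

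Severity: SHOULD-FIX. The goal is a secondary outcome of a proof-of-concept study, and the primary outcome makes no non-inferiority claim.

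**What to change.** 1. **Match the endpoints in 7b.** Apply the published definitions (control with prednisone at or below 7.5 mg daily; oral steroid discontinuation) to study patients and set each beside its own published figure. Take oral prednisone dose from the treatment history, or from the clinical record where the history lacks it. Report control of inflammation alone separately.
2. **Settle the goal, by either route.**
   - *Estimation:* replace the non-inferiority goal with cumulative incidence and its 95% interval beside the published estimate and its interval. State the expected precision (14/20 with nobody lost: 46% to 88%) and that non-inferiority is not claimed.
   - *Non-inferiority kept:* state a justified margin, alpha, a sourced reference rate and one common endpoint. Acknowledge that at n = 20, with equal true rates of 50% to 70% and one-sided 0.025, 80% power needs a margin of about 29 to 35 points.
3. **Reconcile 7b with 7c.** Section 7b names 3 and 6 months, 7c names 6 and 12; 7c adds MUST as a comparator source.

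The cost is wording, confirming that prednisone dose is available, and a small added analysis. No patients or visits are added. The sponsor gives up or qualifies the non-inferiority claim.
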